The study will assess reminding of alcohol's harms using 1 item: "How much does this message remind you that drinking alcohol can be harmful?" Response options will range from not at all (1) to a great deal (5). Higher scores indicate greater reminding of alcohol's harms.

Secondary Outcome: Learning Something New

The study will assess learning something new with 1 item: "Did you learn something new from this message?" Response options will be yes (1) and no (0). Proportion of participants who endorsed learning something new (i.e., answered 1).

STATISTICAL CONSIDERATIONS

General Principles

We will use a two-sided critical alpha of 0.05 to conduct all statistical tests. All confidence intervals presented will be 95% and two-sided. We will use complete case analysis to handle any missing data in analyses of the primary and secondary outcomes. In all analyses, we will use survey weights to account for NORC AmeriSpeak's sampling design and enable results to be representative of the US population of drinkers ages 21+.

Primary Endpoint

The primary outcome is perceived message effectiveness for encouraging people to drink less alcohol. We will measure perceived message effectiveness with 1 item adapted from prior studies: "How much does this message make you want to drink less alcohol?" Response options will range from not at all (1) to a great deal (5).

Hypothesis 1. We hypothesize that all warning topics elicit higher perceived message effectiveness ratings than the control topic.

Secondary Endpoints

The secondary outcomes are reminding of alcohol's harms and learning something new. We will measure reminding of alcohol's harms with 1 item: "How much does this message remind you that drinking alcohol can be harmful?" Response options will range from not at all (1) to a great deal (5). We

will measure learning something new with 1 item: “Did you learn something new from this message?” Response options will be yes (1) and no (0).

Hypothesis 2. We hypothesize that all warning topics elicit higher reminding of alcohol’s harms than the control topic.

Hypothesis 3. We hypothesize that all warning topics elicit higher likelihood of learning something new than the control topic.

Statistical Methods

Analyses of the primary outcome:

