- a. We will use mixed effects linear regression to **evaluate the effect of each warning topic compared to the control topic on the primary outcome of perceived message effectiveness.** We will regress perceived message effectiveness on a set of indicator variables representing each alcohol warning topic (e.g., mouth cancer, liver cancer, etc.), excluding the control topic as the referent. We will treat the intercept as random to account for repeated measures within participants. The coefficients on the warning topics give the average difference in mean perceived message effectiveness between each warning topic and the control topic. Hypothesis 1 will be supported if all coefficients on the warning topics are positive and statistically significant. Given the exploratory nature of the study, we do not plan to adjust p-values for multiple comparisons.
- b. In addition to testing Hypothesis 1, we will also **descriptively rank the warning topics** on the primary outcome of perceived message effectiveness. We will estimate mean perceived message effectiveness for each alcohol warning topic (averaging across messages for each topic) and rank those means.
- c. Finally, we will **descriptively rank the alcohol warning messages** on the primary outcome of perceived message effectiveness. We will estimate means for each alcohol warning message and rank those means.

Analyses of the secondary outcomes:

- a. We will use mixed effects linear regression to **evaluate the effect of each alcohol warning topic compared to the control topic on the secondary outcome of reminding of alcohol’s harms.** We will use the same approach as for the primary outcome (see no. 1 above). We will use mixed effects logistic regression to **evaluate the effect of each alcohol warning topic compared to the control topic on the secondary outcome of learning something new.** We will use the same approach as for the primary outcome, but with a logistic model to account for the binary outcome variable. Hypotheses 2 and 3 will be supported if all marginal effects of the warning topics (vs. control) on the secondary outcomes are positive and statistically significant.
- b. We will **descriptively rank the alcohol warning topics** on the secondary outcomes of reminding of alcohol’s harms and learning something new. We will estimate mean reminding of alcohol’s harms for each alcohol warning topic (averaging across messages for each topic) and

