rank those means. We will also estimate the proportion of participants who indicated they learned something new from each alcohol warning topic and rank those proportions.

c. We will **descriptively rank the alcohol warning messages** on the secondary outcome of reminding of alcohol's harms and learning something new. We will estimate mean reminding of alcohol's harms for each alcohol warning message and rank those means. We will also estimate the proportion of participants who indicated they learned something new from each alcohol warning message and rank those proportions.

We do not plan to conduct moderation analyses.

Sample Size and Power

We plan to collect data from 1,000 participants. We used G*Power to estimate sample size needs.¹ We estimated sample size needs to detect an effect of each warning topic vs. the control topic assuming an alpha=0.05 and correlation among repeated measures of 0.5 (similar to our prior studies of product warnings^{2,3}). We estimated power assuming 2 repeated measures, reflecting that our contrast of interest has two within-subjects levels (warning topic vs. control). Under these assumptions, our sample size will yield >85% power to detect a small standardized effect of Cohen's $f=.05$ (or Cohen's $d=.10$) or larger of each warning topic vs. the control topic. A prior study of alcohol warning topics found effects of this size or larger when comparing perceived message effectiveness of alcohol warning topics vs. control topics.²

Exclusions and Outliers

We will exclude participants who complete <90% of the survey or who complete the survey implausibly quickly (defined as <1/3 of the median completion time).

Interim Analysis

N/A

STUDY INTERVENTION (DEVICE, DRUG, OR OTHER INTERVENTION)

Participants will view warnings about 10 topics: 9 warnings topics and 1 control topic, shown in random order. For each warning topic, participants will view 1 message (selected at random from a pool of 2 messages about that topic) and respond to survey items about that message.

STUDY INTERVENTION ADMINISTRATION (IF APPLICABLE)

Participants will view warnings about 10 topics: 9 warnings topics and 1 control topic, shown in random order. For the control topic and all warning topics except the current US warning (for which there is only 1 message), participants will view 1 of the 2 messages developed for that topic, selected at random. This randomization is accomplished via Qualtrics Randomizer.

SAFETY MANAGEMENT

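### The >85% power at d = .10 is for an unweighted analysis of all 1,000 participants; for the planned weighted analysis it holds only if design effect/(1 − exclusion rate) is 1.11 or less, which the documents do not show

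*Combined protocol and SAP*

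**What the plan says.** Sample Size and Power sets the target ("We plan to collect data from 1,000 participants") and gives the power inputs: "assuming an alpha=0.05 and correlation among repeated measures of 0.5", with two repeated measures because each contrast sets one warning topic against control. It concludes: "Under these assumptions, our sample size will yield >85% power to detect a small standardized effect", namely f = .05 or d = .10 or larger, for each topic. General Principles fixes the test ("We will use a two-sided critical alpha of 0.05 to conduct all statistical tests").

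Two other provisions change what is analysed. General Principles says: "In all analyses, we will use survey weights to account for NORC" AmeriSpeak's sampling design, so that results represent US drinkers aged 21 and over; it also specifies complete-case analysis. Exclusions and Outliers says: "We will exclude participants who complete <90% of the survey or who complete the survey implausibly quickly", the latter meaning under one third of the median time. No design effect, expected spread of weights, exclusion rate or inflated recruitment target appears in the documents.

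**The concern.** None of the listed power inputs covers weighting or exclusions, so the stated power belongs to an analysis that the plan does not run. Unequal weights raise the variance of a weighted mean, and exclusions reduce the number averaged.

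The within-person design does not prevent the weighting loss. It removes between-person variance, and the correlation of .5 already takes credit for that. Every participant rates all ten topics, so with one weight per participant each topic coefficient is in essence a weighted mean of within-person differences, which carries the full design effect.

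At stake is how a non-significant topic is read. If effective N is below 900, the effect detectable with 85% power is larger than the stated d = .10, and a reader who relies on the power statement would credit the contrast with more sensitivity than it has.

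**Working it through.** **Inputs from the documents:** N = 1,000; two-sided alpha .05; correlation ρ = .5; m = 2 measures; f = .05 (d = .10).

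**Assumed, because the documents give no value:** design effect 1.0 to 2.0; exclusion rate x of 0 or 5%, with 10% as a limiting case. Weights are taken to be at participant level and unrelated to the size of the within-person differences.

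**1. The plan's own figure.** Repeated-measures noncentrality: λ = f² × N × m/(1 − ρ) = .0025 × 1,000 × 2/.5 = 10, with 1 and 999 degrees of freedom. Power is 88.5%. Equivalently, the SD of a within-person difference is √(2 × (1 − .5)) = 1 in units of d, so the noncentrality of the paired t is .10 × √1,000 = 3.162, again 88.5%. The >85% is reproduced.

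**2. The planned analysis.** For a weighted mean of differences, the variance is multiplied by the design effect, 1 + CV² of the weights. Hence

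effective N = 1,000 × (1 − x)/design effect, and noncentrality = d × √(effective N).

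**3. The margin.** Two-sided 85% power with 999 degrees of freedom needs a noncentrality of 2.999. At d = .10, effective N = (2.999/.10)² ≈ 900. The statement therefore holds if design effect/(1 − x) ≤ 1,000/900 = 1.11. With no weighting loss, x can reach 10%. With no exclusions, the CV of the weights can reach about .33. For scale, if half the sample carries twice the weight of the other half, CV = (2 − 1)/(2 + 1) = 1/3 and the design effect is 1 + 1/9 = 1.11, which uses the whole margin.

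**4. Power at d = .10, and effect detectable with 85% power, 2.999/√(effective N).**

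| Design effect (assumed) | Effective N, x = 0 | Power | Detectable d | Effective N, x = 5% | Power | Detectable d |
|---|---|---|---|---|---|---|
| 1.0 | 1,000 | 88.5% | .095 | 950 | 86.8% | .097 |
| 1.1 | 909 | 85.4% | .099 | 864 | 83.5% | .102 |
| 1.2 | 833 | 82.2% | .104 | 792 | 80.3% | .107 |
| 1.5 | 667 | 73.2% | .116 | 633 | 71.0% | .119 |
| 2.0 | 500 | 60.8% | .134 | 475 | 58.6% | .138 |

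Exclusions of 10% with no weighting loss leave effective N = 900 and power of 85.0%.

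**5. Check by simulation.** Weighted mean differences with log-normal weights and sandwich standard errors (6,000 trials) gave per-topic power of .885, .849, .742 and .619 at design effects of 1.0, 1.11, 1.5 and 2.0, within about one point of the formula.

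**The case against.** The strongest reply is that the plan makes no arithmetic error and the shortfall rests on inputs that the documents do not contain. Both parts are true. A reader might infer that the power was miscalculated, or that the study is known to have less than 85% power. The documents support neither: 88.5% is right on the listed inputs, and with a design effect of 1.1 and no exclusions the claim survives at 85.4%. What stands is that the plan does not show that the condition is met.

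The exclusion part is weak on its own. It takes more than 10% excluded to break the claim without weighting, and the documents do not settle whether the 1,000 is counted before or after exclusions: Study Duration, Enrollment and Number of Subjects says only roughly 1,000.

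The correlation is also an assumption. Unweighted power is 94.2% at ρ = .6 and 82.2% at ρ = .4, and at .6 the 85% would survive a design effect of about 1.39 without exclusions. Net power could therefore lie on either side of 85%. This limits what can be said about true power, but it does not supply the missing weighting term.

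The practical reach is narrow. The plan expects effects of d = .10 or larger. With 5% excluded, power at d = .12 is about 92% at a design effect of 1.2 and 85% at 1.5; at d = .15 it is about 90% even at 2.0. The planned 95% confidence intervals will also show achieved precision if they are computed with the weights. Even so, d = .10 is the effect at which the plan itself states its power.

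A reader might also attribute low joint power to the weights, since "Hypothesis 1 will be supported if all coefficients on the warning topics are positive and statistically significant". That is mainly a separate matter. If every topic had d = .10, with the shared-control correlation of .5 between contrasts, the chance that all nine are significant is already about 58% with no weighting or exclusions. It comes from the all-nine rule and adds no weight to this point.

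**Conclusion.** Wrong as written: the stated power is for an analysis other than the planned weighted one. The >85% carries over only if design effect/(1 − exclusion rate) is 1.11 or less, and the documents give neither figure. Over the assumed range of design effects from 1.0 to 2.0, per-contrast power at d = .10 runs from 88.5% to 60.8% with no exclusions and from 86.8% to 58.6% with 5% excluded. Weighting, not exclusion, is the main driver.

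The size rests on ρ = .5, on participant-level weights unrelated to the differences, and on design effects that are illustrations and not estimates. The actual loss depends on the weights delivered. The calculation concerns the 1-to-5 rating outcomes; no figure is offered for the binary outcome under Hypothesis 3.

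**What to change.** Ask the panel company for the expected design effect (1 + CV² of the weights) and exclusion rate for this sample. Recompute at effective N = 1,000 × (1 − exclusion rate)/design effect, and replace the >85% sentence in Sample Size and Power with wording such as:

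> For each weighted contrast, power was computed at effective N = 1,000 × (1 − [exclusion rate])/[design effect], using values supplied by the panel company. This gives [ ]% power at d = .10, and 85% power at d = [2.999/√(effective N)].

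Until those values are available, show the range of design effects from 1.0 to 2.0 as in the table above, labelled as assumed, and state that the >85% holds only while design effect/(1 − exclusion rate) is at most 1.11.

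The cost is one enquiry, a short recalculation and possibly a less favourable power statement. No added recruitment is called for on an unknown design effect, and the models, hypotheses and decision rules do not change.

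### Does the sample size section need a power figure for the rule that all nine warning topics must beat control?

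*Combined protocol and SAP*

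**What the plan says.** Under Sample Size and Power, the plan takes 1,000 participants, alpha 0.05 and a "correlation among repeated measures of 0.5". It states its target openly: "We estimated sample size needs to detect an effect of each warning topic vs. the control topic". It uses two repeated measures because "our contrast of interest has two within-subjects levels (warning topic vs. control"). On that basis "our sample size will yield >85% power to detect a small standardized effect", namely Cohen's f = 0.05 or d = 0.10, or larger. As support it adds: "A prior study of alcohol warning topics found effects of this size or larger".

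Under Statistical Methods, primary outcome (a), nine topic indicators are compared with one shared control in a mixed linear model: "We will treat the intercept as random to account for repeated measures within participants". The decision rule is: "Hypothesis 1 will be supported if all coefficients on the warning topics are positive and statistically significant". On multiplicity: "Given the exploratory nature of the study, we do not plan to adjust p-values for multiple comparisons".

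General Principles sets two-sided 95% confidence intervals and survey weights for all analyses. Exclusions and Outliers removes incomplete and implausibly fast responses. The power paragraph mentions neither weights nor exclusions.

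**The concern.** The plan computes power for one comparison but decides its primary hypothesis on nine together. A rule that requires every test to succeed is harder to meet than any one of them, so a reader who takes >85% as the chance of supporting Hypothesis 1 could be well off. If every topic truly works at exactly d = 0.10, the rule fails about 42% of the time, although about eight of the nine contrasts are significant on average. The hypothesis could then be reported as not supported when every warning topic has the planned effect.

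Two further points seem to add weight. The power inputs make no allowance for weighting or exclusions. And the reference number attached to the prior study leads, in the reference list, to a protocol on e-cigarette warnings, so the reader cannot see how far above 0.10 the earlier effects lay.

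**Working it through.** **Inputs from the plan.** n = 1,000; two-sided alpha 0.05; correlation 0.5; d = 0.10 as the minimum effect; nine warning topics and one shared control; no multiplicity adjustment.

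**Assumptions that I add.** The plan gives the 0.5 correlation for a two-measure calculation. I extend it to all ten ratings with equal variances, which is the structure that a random intercept implies. The analysis is unweighted with 1,000 participants analysed. Effects above d = 0.10 are illustrations, because the plan gives no values.

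**Step 1: the plan's own figure.** The standardized paired effect is dz = d/√(2(1 − ρ)) = 0.10/√(2 × 0.5) = 0.10. The noncentrality is 0.10 × √1000 = 3.162. Normal power is Φ(3.162 − 1.960) = 0.885, and the noncentral t gives the same to three decimals. The statement of >85% is therefore correct.

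**Step 2: the joint rule.** Two contrasts that share the control have a covariance of differences equal to half their variance under equal correlation, so the nine z statistics correlate 0.5 with one another. Write δᵢ = dᵢ√1000 for the noncentrality of topic i. Joint power is the integral over a standard normal x of the product, over the nine topics, of Φ((δᵢ − 1.960 + √0.5·x)/√0.5).

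| True effects in the nine topics | Power for all nine |
|---|---|
| all d = 0.10 | 57.7% |
| all d = 0.11 | 71.8% |
| all d = 0.12 | 83.0% |
| all d = 0.13 | 90.8% |
| all d = 0.15 | 98.1% |
| five at 0.10, four at 0.20 | 67.5% |
| three at 0.10, six at 0.20 | 75.5% |
| one at 0.10, eight at 0.20 | 88.5% |
| evenly spread, 0.10 to 0.20 | 84.1% |
| evenly spread, 0.10 to 0.30 | 87.3% |

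Simulated data sets analysed with the random-intercept standard error agree: 57.3% at d = 0.10, 83.2% at 0.12 and 98.0% at 0.15.

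At d = 0.10 throughout, the expected number of significant contrasts is 9 × 0.885 = 8.0. At least eight are significant with probability 76%, and at least seven with probability 85%.

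**Step 3: dependence on the assumed correlation.** With every topic at d = 0.10, changing the common correlation from 0.4 to 0.7 moves joint power from 44% to 90%. Holding warning-versus-control at 0.5 and changing only the correlation between warnings from 0.4 to 0.9 moves it from 53% to 78%. The 58% thus depends on an input that the plan does not state for ten ratings.

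**Step 4: what the data will show.** At correlation 0.5 the standard deviation of a paired difference equals that of one rating. The 95% interval for each topic therefore has a half-width of 1.96/√1000 = 0.062 standard deviations, before weighting. A contrast that misses significance can be read directly from its estimate and interval.

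**Step 5: weights and exclusions.** Per-contrast power of 85% at d = 0.10 needs an effective n of 900. The margin is a design effect of 1000/900 = 1.11 with no loss, or a 10% loss with no weighting effect; a 5% loss alone leaves 86.8%. The documents give no design effect or loss rate, so this is a threshold and not a shortfall.

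**The case for a change.** The strongest case for a change is that the plan does set a supported or not-supported rule for its primary hypothesis, and its only power statement does not address that rule. Calling the study exploratory does not answer this. That phrase explains why p-values are not adjusted, and an all-must-succeed rule costs power rather than alpha. Nor must every topic be weak: three at d = 0.10 with six at 0.20 gives 75.5%. A remedy would take a few sentences and leave the sample size alone.

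The arithmetic stands, and so does the observation that no joint figure appears. What does not stand is that anything depends on it. Readers are not misled, because the sentence that gives >85% is expressly about each topic against control. The Background asks which topics work, and the plan also ranks topics and messages; per-contrast power suits those aims. A failed joint verdict can be understood without a prospective power figure, because the nine estimates and intervals show which topic missed and by how much. They do that better than power computed under an assumed common effect.

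The two side points add little. Weighting and exclusions are real features of the analysis, but the documents contain nothing from which to put a size on them. The reference number is clerical. Reference 1, cited for G*Power, leads to a burden-of-disease paper, and reference 3, cited for prior product-warning studies, to a report on alcohol deaths. Numbering that was carried over from another document would explain all three, and it says nothing about the effect sizes.

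**Conclusion.** No change to the plan is needed. The stated >85% is right (88.5%) for one unweighted contrast with 1,000 participants analysed, and it is presented as such. Power for the all-nine rule is lower when several effects lie near the minimum: about 58% if all nine sit exactly at d = 0.10, about 84% if they spread evenly from 0.10 to 0.20, and 98% if all are 0.15. These figures rest on correlation 0.5 among all ten ratings, equal variances and no weighting. They apply to Hypothesis 1 and do not carry over to the binary outcome of Hypothesis 3.

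What is missing is an extra descriptive figure for a summary verdict. Supplying it would alter no sample size, test, decision rule or estimate. Anyone reporting Hypothesis 1 as not supported can and should show the nine estimates with their intervals beside that verdict, as the plan already provides.
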